Cumulative toxicity is less of a concern when adjunctive LZD is administered for a short duration.³²⁻³⁴ LZD's narrow therapeutic window has tempered the enthusiasm for its therapeutic utility for TB. While most treatment-limiting toxicities, including myelosuppression, gastrointestinal (GI) symptoms and optic neuropathy, are reversible, some, including a painful, sensory-predominant neuropathy, may be permanent.^{35,36} LZD toxicity is driven by both dose and duration.³⁷ In 796 patients with gram-positive bacterial infections on LZD 600 mg BID, hematologic toxicities correlated with treatment duration, occurring in 5% of patients on LZD for 2 to 4 weeks. Peripheral neuropathy occurred in only 3 individuals with a mean treatment duration of 95 days.³⁸ Among 85 patients with DR TB on LZD, the majority of AEs occurred after 2 months.³³ Of 33 patients on LZD 1200 mg for XDR TB, anemia and GI symptoms were common (~50%) but necessitated discontinuation in only 2 patients within the first month.³⁹ No cases of peripheral or optic neuropathy occurred before 2 months. We will use a short course of adjunctive LZD, which has not been studied in a randomized trial for TBM, early in intensive therapy to augment bactericidal activity during the logarithmic growth phase of TB while minimizing cumulative toxicity.

Linezolid and the CSF compartment

CSF to plasma concentration ratios of 0.6 to >0.9 support good to excellent CNS penetration of LZD. However, the distribution of LZD in the CSF, from small studies of mostly neurosurgical patients, varies substantially. After a one-time dose of LZD 600 mg IV, mean CSF maximum concentrations (C_{max}) ranged from 5.1 to 6.6 ug/mL. At steady state, CSF C_{max} was 1.3 to 7.1 and up to 10.8 µg/mL, and minimum concentrations (C_{min}) were <0.2 to 3.1 and up to 6.1 µg/mL. The ability to achieve adequate CSF concentrations for sufficient duration has been inconsistent. One study found CSF LZD concentrations were >4 µg/mL for the entire dosing interval, while in another few patients reached concentrations >1 µg/mL. The minimum inhibitory concentration for 90% of isolates (MIC₉₀) is generally <0.5 µg/mL.

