4.1.7 Randomization

At study entry and prior to the 4th dose of TB treatment, participants will first be randomized by a computer-generated permutated block randomization (block size of 2 or 4) with a 1:1 randomization to high (35 mg/kg) versus standard dose (10 mg/kg) rifampicin. A second 1:1 randomization will then be performed to linezolid 1200 mg daily or no linezolid. Randomization will be stratified by British Medical Research Council (BMRC) TBM disease grade (Table 2), determined at the time of consent, given the association between worse disease severity and higher mortality¹.

Table 2. British Medical Research Council (BMRC) TBM disease grade

GRADE I	Glasgow coma score 15, no focal neurological signs
GRADE II	Glasgow coma score 11–14 with or without focal neurological sign or Glasgow coma score 15 with focal neurological signs
GRADE III	Glasgow coma score \leq 10 with or without focal neurological signs

The randomization schedules will be provided to the site pharmacy in a listed sequence. The sequential, unique randomization code will be recorded on the study entry CRF to assure there is no

skipping of the randomization order. All randomized participants will initiate their allocated study TB treatment within 24 hours of randomization and ideally the same day. For participants from whom informed consent has been obtained, but who are deemed ineligible or who do not enroll into the protocol, a Screening Failure form must be completed and entered into the database.

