10.0 STATISTICAL CONSIDERATIONS

10.1 Sample size estimation

Sample size calculations for the PK analyses are based on different study designs (varying number of participants and time points) using clinical trial simulations. We used the stochastic simulationestimate "sse" methodology for clinical trial simulation and re-estimation to determine sample sizes required to evaluate key PK parameters with precision adequate to determine optimal dosing for a future efficacy trial of LZD. This methodology simulates the data from a planned trial with a proposed design (e.g., number of participants) followed by the estimation of the parameters under the true and alternative models. This is repeated a minimum of 1000 times to estimate PK parameters, standard errors and inter-individual variability. With 30 participants receiving LZD, we will be able to estimate PK parameters with required precision of relative standard errors <10% for typical values and <25% for random effects (inter-individual variability). For the evaluation of LZD adverse events, if we assume 40% of participants in the LZD arm and 10% in the no LZD arm will experience myelosuppression.^{78,84} the planned sample size of 60 participants (n=30 per arm) will provide at least 80% power to detect a similar or greater difference in the frequency of myelosuppression between arms at a significance level of 0.05. Given the modest sample size, we recognize that we may not have adequate power to compare the frequency of myelosuppression in participants on LZD and standard versus high dose RIF; however, if the frequency of myelosuppression in participants on LZD and high dose RIF (n=20) is anticipated as \sim 25%, the 90% confidence interval of this estimate is 10% to 46% with a precision of 18%.

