10.2 Planned analyses

The primary outcomes will be CSF and plasma LZD PK parameters, including CSF to plasma ratio, rate of CSF uptake, and plasma absorption rate constant (k_a), drug clearance (Cl/F), volume of distribution (V_d). We will employ a model-based approach using non-linear mixed effects modeling in NONMEM to estimate plasma and CSF PK parameters based on simultaneous analysis of all plasma and CSF drug concentration data.⁷⁴ We will perform post-hoc Bayesian predictions of secondary LZD PK parameters, including C_{max} , time to C_{max} , AUC₀₋₂₄, and elimination half-life in plasma and in CSF. Based on this approach, we will characterize the dynamic uptake of LZD in the CSF when administered with high and standard dose RIF over 4 weeks and derive a dosing algorithm for LZD to achieve target exposures through simulations. Pharmacodynamic breakpoints for LZD against TB are not established, but we will use target AUC₀₋₂₄, AUC/MIC, T>MIC for LZD of 160 µg*hr/mL, 100, and 85%, respectively.^{23,75,76} We will use sparse sampling to estimate the AUC curve based on CSF sampling early, at steady state, and before LZD discontinuation.⁷⁷

For the LZD adverse event evaluation, the primary outcome will be a dichotomous measure of Grade 3 or higher (yes/no) myelosuppression (e.g., anemia, thrombocytopenia, leukopenia) during the 4 weeks of therapy. A secondary outcome will be LZD discontinuation or dose reduction (yes/no) for any AE. We will compare the frequency of myelosuppression between the LZD and no LZD arms across RIF dosing with the Cochran-Mantel-Haenszel test, which accounts for stratified randomization. Within

the LZD arm, we will explore differences in the frequency of myelosuppression between the standard and two high dose RIF arms combined by a chi-square test. We will use an exposure-response model using logistic regression to test if the probability of myelosuppression and LZD discontinuation is related to PK measurements, including C_{min} , C_{max} and AUC₀₋₂₄.

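### The 80% power for myelosuppression rests on 40% versus 10% with no grade or time window, while the test is of Grade 3 or higher events within 4 weeks, for which the protocol gives no rate

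*Combined protocol and SAP*

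**What the plan says.** Section 10.1 introduces the adverse event calculation with "if we assume 40% of participants in the LZD arm and 10% in the no LZD arm will experience myelosuppression". It concludes that "the planned sample size of 60 participants (n=30 per arm) will provide at least 80% power" to find a difference of that size or larger, "at a significance level of 0.05". It states no grade, no time window and no sidedness.

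Section 10.2 defines the outcome to be tested: "the primary outcome will be a dichotomous measure of Grade 3 or higher (yes/no) myelosuppression", counted over the 4 weeks of therapy. Linezolid is compared with no linezolid by a CMH test across rifampicin dose.

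Three other figures bear on the assumed rates:

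- Section 10.1 adds a precision statement that opens "if the frequency of myelosuppression in participants on LZD and high dose RIF (n=20) is anticipated as" roughly 25%.
- Section 1.0 reports, for patients with gram-positive infections on 600 mg twice daily, that "hematologic toxicities correlated with treatment duration, occurring in 5% of patients on LZD for 2 to 4 weeks".
- Section 1.0 also describes 33 patients on 1200 mg for extensively drug-resistant TB. About half had anaemia and gastrointestinal symptoms, "but necessitated discontinuation in only 2 patients within the first month".

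**The concern.** A power statement is useful only for the outcome that will be analysed. Here the powered event has no grade or window, while the tested event is restricted to Grade 3 or higher within 4 weeks. The 40% also sits poorly beside the 25% in the same paragraph and the 5% in the background, where the argument for a short course is that toxicity is limited.

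Safety and tolerability of 4 weeks of linezolid is the first secondary objective (section 2.3), and the trial is meant to inform linezolid dosing for a Phase III trial (section 1.0). If few severe events occur and the test is not significant, a reader who sees 80% power may take the result as reassurance that the test could not give.

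**Working it through.** **Inputs.** 60 participants, 30 per linezolid group (10.1). The allocation is equal: "A second 1:1 randomization will then be performed to linezolid 1200 mg daily or no linezolid" (4.1.7). With two rifampicin doses this gives 60/4 = 15 per cell. Alpha is 0.05 (10.1), and I assume a two-sided test.

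**Reproducing the stated figure.** Normal approximation with 40% and 10%, pooled rate 0.25:

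- Null SE = √(2 × 0.25 × 0.75 / 30) = 0.1118
- Alternative SE = √((0.40 × 0.60 + 0.10 × 0.90) / 30) = 0.1049
- Power = Φ((0.30 − 1.96 × 0.1118) / 0.1049) = Φ(0.77) = 0.78

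The planned test can be enumerated exactly over four binomials of size 15. In each rifampicin stratum, let a be the linezolid events and m the total events among 30. Then D = a − m/2 and V = 15² × m(30 − m) / (30² × 29) = m(30 − m)/116. The test rejects when (ΣD)²/ΣV ≥ 3.84. At 40% versus 10% the power is 0.80. The continuity-corrected version gives 0.69. The claim therefore reproduces with the uncorrected test, and the normal approximation gives 0.87 one-sided.

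**Comparing the two figures in 10.1.** With equal arms, an average of 40% on linezolid and 25% with high dose rifampicin requires (0.25 + x)/2 = 0.40. So x = 0.55 with standard dose rifampicin, a rate that appears nowhere.

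**Power of the planned test at other rates** (same enumeration, uncorrected, no-linezolid rate 10%):

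| Linezolid + high dose RIF (Arm A) | Linezolid + standard RIF (Arm B) | Power |
|---|---|---|
| 40% | 40% | 0.80 |
| 25% | 55% | 0.81 |
| 25% | 40% | 0.59 |
| 25% | 25% | 0.34 |
| 20% | 20% | 0.20 |
| 15% | 15% | 0.10 |

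For a linezolid rate of 5% or 6%, I varied the no-linezolid rate from 0% to 10%, because no section gives one for this outcome. Power lies between about 0.04 and 0.11. At the 10% end, linezolid has the lower rate. At 5%, the expected number of events on linezolid is 30 × 0.05 = 1.5.

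**Loss to early death.** Section 10.1 makes no allowance, while section 7.4 expects about 40% mortality and section 1.0 places most deaths in the first month. If 12 per cell were evaluable (my assumption), power at 40% versus 10% falls to 0.70.

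**What the blood counts could add.** Under a normal model, moving the share beyond a threshold from 10% to 25% is a shift of 1.282 − 0.674 = 0.61 SD. Adjusting for baseline divides the residual SD by 1/√(1 − r²), so the standardised effect is 0.61/√(1 − r²): 0.70 at r = 0.5 and 0.85 at r = 0.7. With 30 per group, a noncentral t calculation on 58 degrees of freedom (noncentrality = effect × √15) gives 0.76 and 0.90. The binary test gives 0.34 for the same two proportions. The correlations, the normal model and full evaluability are assumptions, and the comparison sets one count against a composite of several lineages.

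**The case against.** The strongest reply is that nothing is miscalculated. The sentence is conditional, claims power only for a difference of similar or greater size, and reproduces. That stands: a reader might infer an arithmetic error, and there is none.

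A reader might also infer that the protocol's own rate for the tested outcome is 5-6% and that this fixes the true power. The documents do not support that. The 5% is ungraded and comes from another population. The 6% (2 of 33) is discontinuation for anaemia or gastrointestinal symptoms, not a myelosuppression rate. These participants are sicker: section 7.4 calls them critically ill and immunosuppressed, those with HIV receive co-trimoxazole (5.7), which 8.1.2 lists as myelosuppressive, and section 10.1 assumes 10% even without linezolid.

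Nor can the 40% and 10% be shown to be any-grade rates. The cited reference numbers (78 and 84) lie beyond a list that ends at 47, as do other citations in section 10, so this looks like a numbering fault.

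The result also depends on the control rate. At 25% on linezolid, power is 0.34 against 10%, 0.63 against 5% and 0.84 against 2%. Low power is therefore a risk, not a demonstrated fact.

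The 25% is attached to n=20, which does not fit 15 per cell and may come from another design. A lower rate with high dose rifampicin also agrees in direction with the hypothesis of lower linezolid exposure (2.0). Both points call for reconciliation; neither supports 40%.

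Finally, the primary endpoints are pharmacokinetic, the 30 linezolid recipients are justified by PK precision, and no passage says that a null result would prove safety. This limits the severity.

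**Conclusion.** The concern holds as a mismatch between the assumption and the outcome, to be fixed before analysis. It does not threaten the primary objective. The 80% is correct for 40% versus 10% but is not shown to apply to Grade 3 or higher myelosuppression within 4 weeks, because no rate for that outcome is given in either arm.

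Against the plan's 10% control rate, power stays near 0.80 only if linezolid recipients average about 40%. It is 0.59 if Arm A has 25% and Arm B 40%, 0.34 if both have 25%, and 0.20 if both have 20%. If the linezolid rate were 5-6%, it would be about 0.1 or less. These values assume 15 evaluable per cell, a two-sided 0.05 level and no continuity correction. Correction or early deaths would lower them; a control rate below 10% would raise those for linezolid rates of 20% or more.

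**What to change.** In 10.1:

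- State that the calculation concerns Grade 3 or higher myelosuppression within 4 weeks, and state the sidedness.
- Replace the single power claim with a short table for linezolid rates from 10% to 40%, preferably at more than one control rate and with an allowance for early death.
- Reconcile 40% with 25%, and correct the citation numbers so that the source can be found.
- Say that a non-significant test does not establish haematological safety.

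In 10.2:

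- Keep the Grade 3+ CMH comparison as the analysis of this outcome. Report the risk difference with its confidence interval, so that the reader sees which excess risks remain compatible with the data.
- Add, as supportive, a mixed model of haemoglobin, log platelets and neutrophil count at Weeks 1, 2 and 4, adjusted for the baseline count and rifampicin arm. The counts are already scheduled (Table 5) and recorded regardless of grade (6.3.13).

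The cost is wording and a modest amount of extra analysis; no new data are needed. The stated power becomes less favourable. A mean shift is less directly clinical than a graded event, which is why the model should sit beside the Grade 3+ result and not replace it. Any gain in power from the model depends on the assumed baseline correlation.

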5.0 STUDY TREATMENT

Participants will be randomized in a factorial design to receive one of the following regimens shown in Table 3.

Arm	Weeks 1-4	Weeks 5-8*	Weeks 9-24*
А	R ₃₅ HZEL		
В	R ₁₀ HZEL	DUTE	D.U
С	R ₃₅ HZE		
D	R ₁₀ HZE		

Table 3: Study treatment regimens

Abbreviations: R, RIF; H, INH; Z, PZA; E, EMB; L, LZD;

*After the first 4 weeks of therapy, participants will receive treatment for TBM as per national guidelines.

Corticosteroid dosing: All participants will receive adjunctive corticosteroids, in addition to pyridoxine 50 mg daily.

Week 1: Dexamethasone IV 0.4 mg/kg/day

- Week 2: Dexamethasone IV 0.3 mg/kg/day
- Week 3: Prednisone PO 60 mg/day
- Week 4: Prednisone PO 50 mg/day
- Week 5: Prednisone PO 40 mg/day
- Week 6: Prednisone PO 30 mg/day
- Week 7: Prednisone PO 20 mg/day
- Week 8: Prednisone PO 10 mg/day

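### Precision for myelosuppression on linezolid plus high-dose rifampicin is computed on 20 participants, but the 2x2 design expects about 15, in one arm rather than two

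*Combined protocol and SAP*

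**What the plan says.** Section 4.1.7 sets out two successive randomisations. The first is "with a 1:1 randomization to high (35 mg/kg) versus standard dose (10 mg/kg) rifampicin". Of the second it says: "A second 1:1 randomization will then be performed to linezolid 1200 mg daily or no linezolid". Table 1 in the synopsis and Table 3 in section 5.0 list four arms, and Arm A (R35HZEL) is the only one that contains both linezolid and high-dose rifampicin. There is a single high dose level.

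Section 10.1 relies on "the planned sample size of 60 participants (n=30 per arm") for the comparison of linezolid with no linezolid, and its pharmacokinetic precision claim begins "With 30 participants receiving LZD". It then concedes that power may be inadequate to compare rifampicin doses among linezolid recipients. In place of power it offers a precision statement for the "frequency of myelosuppression in participants on LZD and high dose RIF (n=20"): if that frequency is about 25%, "the 90% confidence interval of this estimate is 10% to 46% with a precision of 18" percent.

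Section 10.2 plans the matching exploratory analysis. Restricted to linezolid participants, "we will explore differences in the frequency of myelosuppression between the standard and two high dose RIF arms combined by a chi-square test".

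**The concern.** Two statements in the statistical section do not fit the trial that the rest of the document describes. If 20 of the 30 linezolid participants are on high-dose rifampicin, only 10 are on standard dose. That is a 2:1 split, and no section provides for one. A pooling of two high-dose arms among linezolid recipients also needs an arm that does not exist: the trial's other high-dose arm, Arm C, receives no linezolid.

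At stake is the only precision the plan states for the myelosuppression rate under linezolid with high-dose rifampicin. Section 7.6 says the adverse event endpoint is meant to assess linezolid toxicity alongside both rifampicin doses, so this group matters. As printed, its precision looks better than the design delivers, and the section 10.2 comparison cannot be run literally.

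**Working it through.** **Inputs**
- Total sample size 60, with 30 on linezolid and 30 not: section 10.1.
- Allocation 1:1 for rifampicin dose, then 1:1 for linezolid: synopsis and section 4.1.7.
- Four arms, one of them linezolid plus high-dose rifampicin: Tables 1 and 3.
- Late exclusions are replaced to keep the arms balanced: section 3.3.
- Anticipated frequency about 25%, confidence level 90%, stated n of 20: section 10.1.

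**Step 1. Expected size of Arm A**

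60 × 1/2 × 1/2 = 15. The documents do not print this figure, and the realised number may differ somewhat. If n were 20, the standard-dose linezolid group would be 30 − 20 = 10.

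**Step 2. Reproduce the stated interval**

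The exact (Clopper-Pearson) two-sided 90% interval for x events in n has
- lower limit = 5th percentile of Beta(x, n − x + 1)
- upper limit = 95th percentile of Beta(x + 1, n − x).

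For 25% of 20, x = 5. The limits are 10.4% and 45.6%, and the half-width is (45.6 − 10.4)/2 = 17.6 points. These round to the stated 10%, 46% and 18%. Other 90% methods for 5/20 do not match: Wilson gives 12.7% to 43.2%, and the simple normal interval 9.1% to 40.9%. The plan therefore used the exact method on 20 participants. The 20 is not a typing slip beside a calculation done on 15.

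**Step 3. Repeat with 15**

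A quarter of 15 is 3.75, which is not a possible count, so the whole counts on either side are shown as well.

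| Events / n | Observed | Exact 90% interval | Half-width |
|---|---|---|---|
| 5/20 (as in the plan) | 25.0% | 10.4% to 45.6% | 17.6 points |
| 3/15 | 20.0% | 5.7% to 44.0% | 19.1 points |
| 3.75/15 (nominal 25%) | 25.0% | 8.6% to 49.3% | 20.4 points |
| 4/15 | 26.7% | 9.7% to 51.1% | 20.7 points |

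**Step 4. Compare sections 10.1 and 10.2**

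The two odd statements agree with each other. Three equal rifampicin groups among 30 linezolid participants (one standard, two high dose) would give 30 × 2/3 = 20 on high dose. They may come from a three-group layout, but that is inference; the documents do not say so. What can be established is that both contradict the two 1:1 randomisations and the four listed arms.

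**The case against.** The best reply is that little depends on this number. The stated precision moves by about 1.5 to 3 points. No sample size, stopping rule or primary analysis uses it. Section 10.1 already warns that power for this contrast may be inadequate, and section 10.2 calls the comparison exploratory. Section 10.1 also words the contrast plainly as standard versus high-dose rifampicin on linezolid, so an analyst would almost certainly arrive at Arm B versus Arm A. Finally, the trial does contain two high-dose arms, A and C, and at 3/15 the upper limit of 44.0% lies below the plan's 46%.

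Most of this stands, and it limits how serious the point is. It does not remove the contradiction. Arm C cannot enter a comparison confined to linezolid recipients. All high-dose participants together (A plus C) would number about 30, so that reading does not give 20 either. The point about 3/15 concerns where the interval sits: its width is still greater than the plan states. An analyst's likely guess is also no substitute for a plan that names its groups.

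**Conclusion.** The concern holds. The linezolid plus high-dose rifampicin group is expected to number about 15, not 20, and only one such arm exists. The interval in section 10.1 is correctly computed for 5/20 but rests on the wrong denominator. At 15 participants the precision is about 19 to 21 points instead of 18. The comparison in section 10.2 would be about 15 versus 15, not 20 versus 10.

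This assumes that all 60 are enrolled with both 1:1 ratios met, that the anticipated frequency stays near 25%, and that the exact method is kept. The consequence is modest. The pharmacokinetic sample size and the comparison of 30 on linezolid with 30 not on it do not depend on the figure of 20. It should still be corrected, because a stated precision is wrong and a planned comparison names an arm that is not there.

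**What to change.** - **Section 10.1:** replace the n of 20 with an expected number of about 15 (Arm A). Restate the exact 90% interval using achievable counts: 5.7% to 44.0% for 3/15 and 9.7% to 51.1% for 4/15, with a precision of about 20 points. If a single nominal 25% figure is preferred, it is about 9% to 49%, marked as not a whole count.
- **Section 10.2:** define the exploratory comparison among linezolid participants as Arm A (R35HZEL) versus Arm B (R10HZEL), and keep the exploratory label. A risk difference with its confidence interval would be a useful addition, and an exact test is an option at about 15 per group; neither is needed to cure the inconsistency.

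The cost is a change of wording in two sections and a slightly less favourable stated precision. No participants, procedures or changes to trial conduct are added.
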